If appropriate, the PK relationship between the treatment doses and plasma exposure (trough concentrations and C_{max}) of mesdopetam and its metabolites will be assessed using a power model.

Safety analyses

Safety evaluations include AE and concomitant medication reporting, complete physical examination, vital signs, 12-lead ECG, C-SSRS and clinical safety laboratory tests (serum chemistry, haematology, urinalysis and coagulation). All will be presented as data summaries. No formal statistical analyses will be performed.

AEs (overall, by seriousness, by severity, by relationship) and concomitant medications (overall) recorded throughout the investigation will be reported following classification according to Medical dictionary for Regulatory Activities (MedDRA) System Organ Class (SOC) and Preferred Term (PT) and World Health Organisation Drug dictionary (WHODD) Anatomical Therapeutic Chemical (ATC) Classification System respectively.

All other safety evaluations performed at screening and Visits 1-6 (EOS/EW) will be summarized accordingly.

Unscheduled safety laboratory samples assayed at the local hospital will be listed according to Site.

Confidential	Version: 5.0	Page 14 of 74
Protocol: IRL790C005	Date: 5 Mar 2021	e

Schedule of study and study procedures

Visit	Screening	Phone calls	Visit 1 (Baseline)	Visit 2	Phone call	Phone calls	Visit 3	Phone calls	Visit 4	Phone calls	Visit 5 (EOT)	Visit 6 (EOS/EW)
		Baseline diary period	Dose run-in				Treat	nent period	l			Follow up
Day	-56 to -10	-9 to -1	Day 1	9	14	21	28		56		84	
Week				Week 1	2	3	4	7	8	11	12	5-8 days after EOT
Time window	-	_2	-	+ 2 days	±2 days	± 2 days ²	±4 days	_2	±4 days	_ ²	-2 to 0 days	
Informed Consent	Х								X ³			
Demographics/Medical History	Х											
Inclusion/Exclusion Criteria	Х		Х									
Hoehn and Yahn scale	Х											
Concomitant Medication	Х	Х	Х	Х	Х	Х	Х	Х	Х	Х	Х	Х
Height	X											
Weight	X											Х
Vital Signs (incl supine/standing BP)	Х		X ⁵				Х		Х		Х	Х
Physical Examination	Х										Х	Х
12-lead ECG	X ⁴		X ⁵						Х		Х	Х
Haematology / Clinical Chemistry	X		X ⁵						Х		Х	Х
CYP2D6 genotyping									Х			
Dipstick Urinalysis	Х		X ⁵						Х		Х	Х
Pregnancy Test ^{6/6a}	X ⁶		X^6				X ^{6a}		X^{6a}		X ⁶	
MDS-UPDRS	X ⁷		Х				X ⁸		Х		Х	
24-hour patient home diary training	X9											

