⁹ Diary concordance training (takes approx. 2.5 hours). Could be done either at the screening visit or during a separate scheduled visit after receipt of the screening lab results and prior start of the baseline diary completion period.

Confidential	Version: 5.0	Page 15 of 74
Protocol: IRL790C005	Date: 5 Mar 2021	C C

¹ Safety follow-up visit to be performed (if possible) for early IMP discontinuations (5-8 days after last dose of IMP)

² Site to call the patient the working day before the first 24-hour diary completion period, as a reminder, and the working day after the last 24-hour diary completion period to encourage compliance.

³ CYP2D6 genetic informed consent must be signed prior CYP2D6 blood sample testing. Note: the CYP2D6 testing is optional

⁴ Triplicates separated by at least one minute

⁵ If 29 days or more between the Screening visit and Visit 1 (Baseline), safety parameters (Vital Signs, single ECG, Haematology/Clin Chem and Urinalysis) are included also at Visit 1 (Baseline).

⁶ Serum hCG; Only applicable for women with childbearing potential (as defined in section 8.1)

^{6a} Urine hCG; Only applicable for women with childbearing potential (as defined in section 8.1)

⁷ Part 4 question 4.2

⁸ Part 2 (M-EDL) and part 4 questions 4.1 and 4.2

Visit	Screening	Phone calls	Visit 1 (Baseline)	Visit 2	Phone call	Phone calls	Visit 3	Phone calls	Visit 4	Phone calls	Visit 5 (EOT)	Visit 6 (EOS/EW)
		Baseline diary period	Dose run-in				Treat	nent period	l			Follow up
Day	-56 to -10	-9 to -1	Day 1	9	14	21	28		56		84	
Week				Week 1	2	3	4	7	8	11	12	5-8 days after EOT
Time window	-	_2	-	+ 2 days	±2 days	± 2 days ²	± 4 days	_2	± 4 days	_2	-2 to 0 days	
24-hour patient home diaries hand out/collection	X ¹⁰		X ^{10 11}				X ^{10 11}		X ^{10 11}		X ¹¹	
24-hour patient home diary entry ¹²		Х				Х		Х		Х		
Patient motor function review							Х					
Modified UDysRS			Х				Х		Х		Х	
MMSE	X										Х	
CGI-S			Х				Х		Х		Х	
C-SSRS			Х				Х		Х		Х	
Adverse Event (AE)	Х	Х	Х	Х	Х	Х	Х	Х	Х	Х	Х	Х
Serious Adverse Event (SAE) collection/reporting	Х	Х	Х	Х	Х	Х	х	Х	Х	Х	Х	Х
Randomization ¹³			Х									
PK sample ¹⁴									Х		Х	
Dispense IMP			Х	Х			Х					
Collect empty bottles of IMP				Х			X ¹⁵		Х		Х	
Compliance				Х	Х	Х	Х	Х	Х	Х	Х	

Confidential	Version: 5.0	Page 16 of 74
Protocol: IRL790C005	Date: 5 Mar 2021	C

¹⁰ Three empty diaries handed out

¹¹ Three completed diaries collected

 ¹² Three completed diaries conjected

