11.1.5. Vital Signs

Pulse and systolic/diastolic BP will be measured in supine position after five minutes of rest and then after 1 minute and 3 minutes in standing position, without sitting in between. Any symptomatic orthostatic reaction will be noted in the CRF (no/yes).

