12.3. Expectedness

An expected adverse reaction is an adverse reaction, the nature or severity of which is consistent with the applicable product information (Investigator's Brochure [8]), otherwise it is considered unexpected.

Based on non-clinical safety data in experimental animals as well as on Phase 1 data in healthy male volunteers and in patients with advanced PD (Phase 2a), AEs are likely to predominantly be CNS related. Adverse reactions in patients with advanced PD are listed below:

Table 4: Potential AEs associated with mesdopetam treatment	

Nervous system	Cardiac	General disorders and administration site condition	Musculoskeletal and connective tissue disorders
Parkinsonism	Postural dizziness	Lethargy	Muscular weakness
Tremor	Dyspnoea	Fatigue	
Muscular rigidity		Oedema	
Insomnia			
Somnolence			
Headache			
Slurred thinking			
Dissociation			
Balance disorder			
Dizziness			
			I
Confidential		Version: 5.0	

Confidential	Version: 5.0	Page 56 of 74
Protocol: IRL790C005	Date: 5 Mar 2021	6

Nervous system	Cardiac	General disorders and administration site condition	Musculoskeletal and connective tissue disorders
Concentration difficulties			
Gait freezing			
Fall			

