14.10.5. Vital signs

For BP and pulse rate, descriptive statistics of actual values and change from baseline will be summarized by treatment group and assessment day. Categorically classified (Normal/Abnormal) results will also be summarized.

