6.2.9 Vital Signs

For blood pressure and pulse rate, the orthostatic changes will be calculated as standing minus supine readings. Patients meeting the following criteria will be identified:

- Patients with > 20 mmHg reduction (standing minus supine) in systolic blood pressure at 1 minute or 3 minutes of standing.
- Patients with > 10 mmHg reduction (standing minus supine) in diastolic blood pressure at 1 minute or 3 minutes of standing.

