6.17.3 Vital Signs

Descriptive statistics for observed values and changes from baseline in the following vital signs will be presented by treatment group and visit:

- Systolic blood pressure (mmHg)
- Diastolic blood pressure (mmHg)
- Pulse rate (bpm)
- Body weight (kg)

Both standing and supine values, as well as orthostatic changes (standing – supine) will be presented for blood pressure and pulse rate. Measurements taken either seated or prone will be considered taken supine. The number and percentage of patients with either >20 mmHg reduction in systolic blood pressure after standing, or >10 mmHg reduction in diastolic blood pressure after standing, or both will be summarized. All vital sign data will be listed.

QMD Ref: Worldwide-TMP-ST-005-7.0 Effective: 12Aug2019	Governing QMD: Worldwide-SOP-ST-001	
Confidentiality Statement		
This document is the property of Worldwide Clinical Trials Inc. and may not be duplicated, copied, altered or removed from company without prior approval from Worldwide Quality Assurance or in compliance with Worldwide Standard Operating Procedures.		
REF: Worldwide-TMP-QA-001f-1.3	Page 44 of 49	

Worldwide Clinical Trials Controlled Quality Management Document		
WORLDWIDE CLINICAL TRIALS	Sponsor:	Integrative Research Laboratories Sweden AB
	Protocol Number:	IRL790C005
STATISTICAL ANALYSIS PLAN. PHASE 2-3-4		

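### SAP 6.17.3 names no table for the solicited orthostatic-symptom item and does not split its >20/>10 mmHg count by baseline status, so new drops by dose are diluted by pre-existing ones

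*SAP*

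**What the plan says.** **Collection.** Protocol 11.1.5 measures pulse and blood pressure supine and again after 1 and 3 minutes standing, and adds: "Any symptomatic orthostatic reaction will be noted in the CRF (no/yes"). The schedule places vital signs at screening and Visits 3, 4, 5 and 6. Visit 1 is conditional: "If 29 days or more between the Screening visit and Visit 1 (Baseline), safety parameters" are repeated there.

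**Definition.** SAP 6.2.9 identifies "Patients with > 20 mmHg reduction (standing minus supine) in systolic blood pressure at 1 minute or 3 minutes of standing", with a matching diastolic limit of more than 10 mmHg. Neither limit refers to the patient's status before treatment.

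**Tables.** SAP 6.17.3 plans "The number and percentage of patients with either >20 mmHg reduction in systolic blood pressure after standing", or over the diastolic limit, or both. It also states: "Both standing and supine values, as well as orthostatic changes (standing – supine) will be presented for blood pressure and pulse rate". Those measures are summarised as observed values and changes from baseline by group and visit. The symptom item is not named in SAP 6.2.9 or 6.17.3, although all vital-sign data go to a listing.

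**Protocol analysis.** For blood pressure and pulse, protocol 14.10.5 says: "Categorically classified (Normal/Abnormal) results will also be summarized". SAP 6.17.3 has no such summary, and its removal is not among the 14 changes listed in SAP section 9.

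**Risk context.** Table 4 in protocol 12.3 includes "Postural dizziness" among the potential adverse events of mesdopetam.

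**The concern.** A safety reader wants to know how many patients developed an orthostatic drop on each dose who did not have one before, and how many had symptoms when they stood up. The planned count does not isolate the first group, and no named table gives the second.

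The baseline point matters because entry excludes orthostatic hypotension only when it is symptomatic and clinically significant (exclusion criterion 11). Patients with asymptomatic drops can be randomised. If many are, the threshold count on treatment consists largely of drops that were already there.

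The symptom item matters because it is a fixed question tied to a standing test. Adverse events, by contrast, are preferably elicited by open, non-leading questions (protocol 12.1), and no rule says that a yes on the vital-signs form must be entered as an adverse event.

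**Working it through.** The documents state no orthostatic rate, so there is no figure of the plan's own to reproduce. The check has two parts.

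**1. Comparison within SAP 6.17**

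| Data | Separation of baseline from post-baseline |
|---|---|
| Laboratory and urinalysis (6.17.2) | Shift tables from baseline |
| ECG (6.17.4) | Separate bands for baseline values, post-baseline values and increases; shift of overall interpretation |
| Physical examination (6.17.5) | Shift tables |
| C-SSRS (6.17.6) | Shift table |
| Orthostatic limits (6.17.3) | Number and percentage only |
| Symptom item (6.17.3) | Not named |

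The orthostatic limits are the exception. A baseline exists for them: SAP 6.2.2 takes the last non-missing value before first dose, which is screening, or Visit 1 when vital signs were repeated there.

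**2. Size of the dilution (illustration; all rates assumed)**

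Let b be the proportion meeting the limit at baseline, all of whom are assumed to stay over it, and i the proportion of the rest who newly meet it. The planned count then shows b + (1 − b) × i.

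With i = 15% on active and 5% on placebo, the new-onset ratio is 3 at every b:

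| b | Active | Placebo | Ratio in planned count |
|---|---|---|---|
| 20% | 0.20 + 0.80 × 0.15 = 32.0% | 0.20 + 0.80 × 0.05 = 24.0% | 1.33 |
| 30% | 0.30 + 0.70 × 0.15 = 40.5% | 0.30 + 0.70 × 0.05 = 33.5% | 1.21 |
| 40% | 0.40 + 0.60 × 0.15 = 49.0% | 0.40 + 0.60 × 0.05 = 43.0% | 1.14 |

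A second assumed pair, 25% versus 10% (new-onset ratio 2.5), gives planned-count ratios of 1.71, 1.43, 1.28 and 1.20 at b = 10%, 20%, 30% and 40%.

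**Excess in patients.** At 35 per arm, b = 30% and the first pair of rates, the planned count shows (0.405 − 0.335) × 35 = 2.45 extra patients. The new-onset count shows (0.15 − 0.05) × 24.5 = 2.45. The expected excess is the same, so the planned comparison is diluted, not biased.

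**Noise.** The enlarged sample is 154, about 38 per arm. The standard error of a chance difference in baseline prevalence between two arms is √(2b(1 − b)/38): 6.9, 9.2, 10.5 and 11.2 percentage points at b = 10%, 20%, 30% and 40%. At b = 30% and the first pair of rates:

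- Planned count: difference 7.0 points; SE = √(0.405 × 0.595/38 + 0.335 × 0.665/38) = 11.0 points; 7.0/11.0 is about 0.6.
- New-onset count: 0.70 × 38 = 26.6 at risk per arm; difference 10.0 points; SE = √(0.15 × 0.85/26.6 + 0.05 × 0.95/26.6) = 8.1 points; 10.0/8.1 is about 1.2.

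Conditioning on baseline removes noise as well as changing the ratio. The expected new-onset counts are only about 4 and 1 patients per arm, so both remain descriptive.

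**The case against.** A reader might infer that new symptomatic orthostatic effects by dose will not be reported at all. The documents do not support that, for four reasons:

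- Symptoms recorded as adverse events that start or worsen after first dose enter the TEAE tables by system organ class and preferred term. Safety outputs are given by actual treatment group and by adjusted dose group (SAP 6.17 and 6.17.1).
- The standing-minus-supine change is summarised against baseline by group and visit, so a general shift would show.
- SAP 6.3.6 says that observed data are summarised unless stated otherwise, and SAP 6.3.4 gives frequency and percent for categorical variables. Together these arguably reach the symptom item, and the detailed layouts may sit in table shells that are not part of these documents.
- The protocol reports vital signs as unaffected by mesdopetam in Phase 2a, and its safety analyses are descriptive.

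All of this stands, and it limits the point. None of it closes the gap completely. A mean change can conceal a minority with large drops and says nothing about symptoms. TEAE tables depend on a yes being entered as an adverse event, and related terms may be split across categories. The general rule sets no denominator, baseline handling or link to the blood-pressure limits.

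The argument that the excess number of patients is unchanged is correct in expectation. It does not address chance baseline imbalance, which a shift table handles directly.

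**Conclusion.** The point holds as a reporting improvement of low severity. No table is specified for the solicited symptom item, and the >20/>10 mmHg count is not split by baseline status, so new-onset drops by dose are diluted by pre-existing ones.

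The ratios of 1.2 against 3 rest on assumed rates and on every baseline drop persisting. If fewer drops existed at baseline, or some resolved, the dilution would be smaller. The documents do not say how common such drops are in this population.

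Efficacy, type I error and sample size are unaffected. The missing Normal/Abnormal summary is a separate, smaller matter: it is a departure from the protocol that SAP section 9 does not record.

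**What to change.** In SAP 6.17.3, from data already in the CRF:

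1. Present the >20/>10 mmHg criterion as a baseline-to-visit shift table by actual and adjusted dose group. Add the number newly meeting it, with patients not meeting it at baseline as the denominator.
2. Tabulate the yes/no symptom item by dose group and visit.
3. In both tables, show Visits 3 to 5 separately from Visit 6, which falls 5 to 8 days after the last dose.
4. Restore the Normal/Abnormal vital-sign summary from protocol 14.10.5, or list its removal in SAP section 9.

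The cost is a few lines of SAP text and two small tables, plus the summary in item 4 if it is restored. No new data are needed, and no clinical rule changes.

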6.17.4 Electrocardiogram Data

Descriptive statistics for observed values and changes from baseline in the following ECG variables will be presented by treatment group and visit:

- Heart rate (bpm)
- PR interval (ms)
- QRS duration (ms)
- OT interval (ms)
- QTc interval (ms)
- QTcB interval (ms) [Bazett's formula]
- QTcF interval (ms) [Fridericia's formula]
- RR interval (ms) •

Shift tables in relation to the overall interpretation i.e., Normal, Abnormal NCS (Not Clinically Significant), and Abnormal CS (Clinically Significant) from baseline to each follow-up visit will be presented.

Any QTcF or QTcB Interval (ms) result meeting the following criteria will be identified as an electrocardiogram abnormality and a separate tabulation by treatment group will be provided:

- Interval at Baseline of >450 msec and \leq 480 msec
- Interval at Baseline of >480 msec and \leq 500 msec
- Interval at Baseline of >500 msec
- Post-Baseline value of >450 msec and < 480 msec
- Post-Baseline value of >480 msec and \leq 500 msec
- Post-Baseline value of >500 msec
- Post-Baseline increase of >30 msec and < 60 msec
- Post-Baseline increase of >60 msec

All ECG data, including details of any abnormalities, will be listed.

6.17.5 Physical Examination

Shift tables for the observed change in status of each of the body systems, (Normal, Abnormal NCS, and Abnormal CS) from baseline to each follow-up visit will be tabulated by treatment group. All data, including details of clinically significant findings will be listed.

6.17.6 C-SSRS

C-SSRS outcomes (Suicidal Ideation and Suicidal Behaviour) since baseline will be tabulated by treatment group and overall, by visit. A shift table for the change in number and percent of patients in each category (No Suicidal Ideation or Behaviour, Suicidal Ideation, Suicidal Behaviour) from baseline to each visit will be presented. Patients with both Suicidal Ideation and Suicidal Behaviour will be included in the Suicidal Behaviour category.

All reported data will be listed.

6.17.7 Features of Dopamine Dysregulation Syndrome, MDS-UPDRS Question 1.6

MDS-UPDRS Question 1.6 will be completed at all in-person visits, (excluding Day 9 and Day 28) up to end of treatment. A shift table for the change from baseline in number and percent of patients rated in each score category (0 to 4) will be presented by treatment group and visit. Percentages will be based on the number of patients with non-missing score at baseline and post-baseline for the relevant visit. Descriptive statistics for the score as a continuous measure for observed values and change from baseline to each post-baseline visit will be provided and the number and percent of patients with a worsening post-baseline score of 2 or more points will also be presented.

6.17.8 Pregnancy

Pregnancy testing will be performed at Screening, Visit 1, Visit 3, Visit 4, and Visit 5 for women of childbearing potential. Patient counts within each category (positive/negative test result) will be summarized by visit. All pregnancy testing data will be listed. Any reported pregnancies and details of the condition of neonate(s) will be provided as separate listings.

7 INTERIM ANALYSIS

No interim analyses are planned for this study.

8 DATA SAFETY MONITORING BOARD ANALYSIS

No data safety monitoring board (DSMB) analyses are planned for this study.

QMD Ref: Worldwide-TMP-ST-005-7.0 Effective: 12Aug2019	Governing QMD: Worldwide-SOP-ST-001	
Confidentiality Statement		
This document is the property of Worldwide Clinical Trials Inc. and may not be duplicated, copied, altered or removed from company without prior approval from Worldwide Quality Assurance or in compliance with Worldwide Standard Operating Procedures.		
REF: Worldwide-TMP-QA-001f-1.3	Page 46 of 49	

Worldwide Clinical Trials Controlled Quality Management Document		
WORLDWIDE	Sponsor:	Integrative Research Laboratories Sweden AB
CLINICAL TRIALS	Protocol Number:	IRL790C005

STATISTICAL ANALYSIS PLAN. PHASE 2-3-4

9 CHANGES TO PLANNED PROTOCOL ANALYSIS

- 1. The primary efficacy analysis will be adjusted for country and weighted by the number of subjects participating from each country to account for any observed imbalances in recruitment across countries.
- 2. Analyses will be conducted for individual active dose and pooled doses.
- 3. Secondary and exploratory endpoints have been itemized separately compared to the protocol for clarity.
- 4. Key Secondary Efficacy Endpoints were defined:
 - Change from baseline with mesdopetam compared to placebo in ON-phase dyskinesia assessed by MDS-UPDRS part 4 question 4.2 (Functional impact of dyskinesias).
 - Change from baseline with mesdopetam compared to placebo in disability associated with ON-phase dyskinesia assessed with the sum score of parts 1b and 4 of the UDysRS.
- 5. Other Key Secondary Efficacy Endpoints were defined:
 - Change from baseline with mesdopetam compared to placebo in motor symptoms of PD assessed with MDS-UPDRS total score of part 2 (M-EDL).
 - Change from baseline with mesdopetam compared to placebo in average daily OFF-time.
- 6. Exploratory endpoint added to reflect protocol section 14.7. Efficacy endpoints, Table 6 Other endpoints:
 - Change from baseline with mesdopetam compared to placebo in the total scores for each component part of the MDS-UPDRS (Part 1, Part 3, and Part 4).
 - Change from baseline with mesdopetam compared to placebo in freezing and freezing of gait, assessed by MDS-UPDRS: Question 2.13 + Question 3.11.
- 7. Safety endpoint added to reflect protocol section 14.7. Efficacy endpoints, Table 6 Other endpoints:
 - Change from baseline with mesdopetam compared to placebo in features of dopamine dysregulation syndrome assessed by MDS-UPDRS Question 1.6.
- 8. Improvement in Daily ON-time, Responder Analysis
- 9. PK Analysis Set was defined.
- 10. CYP Genotype Subset was defined.
- 11. Multiplicity strategy was refined to address Key Secondary Endpoints.

QMD Ref: Worldwide-TMP-ST-005-7.0 Effective: 12Aug2019	Governing QMD: Worldwide-SOP-ST-001	
Confidentiality Statement		
This document is the property of Worldwide Clinical Trials Inc. and may not be duplicated, copied, altered or removed from company without		
prior approval from Worldwide Quality Assurance or in compliance with Worldwide Standard Operating Procedures.		

Worldwide Clinical Trials Controlled Quality Management Document		
WORLDWIDE CLINICAL TRIALS	Sponsor:	Integrative Research Laboratories Sweden AB
	Protocol Number:	IRL790C005
STATISTICAL ANALYSIS PLAN. PHASE 2-3-4		

- 12. Exposure calculation was redefined.
- 13. Compliance calculated was redefined
- 14. Analysis of the primary and key secondary endpoints will be repeated using the modified stratification factor.

QMD Ref: Worldwide-TMP-ST-005-7.0 Effective: 12Aug2019	Governing QMD: Worldwide-SOP-ST-001	
Confidentiality Statement		
This document is the property of Worldwide Clinical Trials Inc. and may not be duplicated, copied, altered or removed from company without prior approval from Worldwide Quality Assurance or in compliance with Worldwide Standard Operating Procedures.		
REF: Worldwide-TMP-QA-001f-1.3	Page 48 of 49	

Worldwide Clinical Trials Controlled Quality Management Document		
WORLDWIDE CLINICAL TRIALS	Sponsor:	Integrative Research Laboratories Sweden AB
	Protocol Number:	IRL790C005
STATISTICAL ANALYSIS PLAN. PHASE 2-3-4		

